Neurological examination	X	X	X	X	X	X
Recording of contraceptive method	X ^E					
Haematology, Blood chemistry, Urinalysis ^L	X		X		X	X
Pregnancy test	X ^F	X ^G				
Administration of EDSS	X	X	X	X	X	X
Inclusion and Exclusion criteria	X	X				
Administration of 25-FWT; 9HPT; Low Contrast Letter Visual Acuity Test; Symbol Digit Modalities Test	X	X	X	X	X	X
Administration of MFIS and Fatigue Severity Scale	X	X	X	X	X	X
Randomisation		X				
Neurophysiological assessments ^H		X	X	X	X	X
Immunological assessments ^I		X	X	X		X
Brain MRI ^L	X	X			X	X
12-lead ECG ^L	X				X	X
IP dispensing		X	X	X		
IP returning and compliance			X	X	X	X
Adverse Events ^M	X	X	X	X	X	X
Reason for study termination						X

25-FWT = 25-foot Timed Walk; 9HPT = 9 Hole PEG Test

A - Early Termination (ET) Visit is applicable for the patient that withdraws from the study at any time: they will undergo all assessments requested at the ET Visit as soon as possible after injection.

B - Prior to performing any study assessment (not part of the patient routine medical care).

C - Includes medications in the last 12 weeks

D - Includes height, weight, body mass index (BMI), waist circumference, vital signs (blood pressure and heart rate)

E - Only for female patient: if the patient is post-menopausal the age at menopause will be documented

F - Only for female patient: serum pregnancy test is not required if the patient is post-menopausal or surgically sterilized

G - Only for female patient: urine pregnancy test is not required if the patient is post-menopausal or surgically sterilized, or if a serum pregnancy test was performed within 7 days before Baseline (Visit 0)

H - To be performed at the centre of PPD [REDACTED], only in patients without relapse

I - Immunological assessments will include immune phenotype and immunometabolic analysis. The blood sampling must be done before receiving corticosteroids in the scheduled 80 patients with (40 patients) or without relapse (40 patients) enrolled in the sites of Rome, Naples and Pozzilli

L - Whenever it will be available according to local clinical practice

M - Recording of Adverse Events will start at signature of informed Consent

2

Sponsor, Investigators and Study Administrative Structure

This clinical study will be sponsored by Merck Serono S.p.A., [name].

The study will be conducted at approximately 18 sites in Italy, with competitive enrolment. Sites will be Academic or Hospital Neurological Departments.

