5.3.1 Inclusion Criteria

All patients (with or without relapse) must fulfil all of the following criteria to be eligible for this study:

- Males and females between 18 and 55 years of age;
- Patients with RRMS, according to the revised McDonald Criteria (2010) (Polman et al, 2011);
- Patients with an expanded disability status scale (EDSS) score between 0 and 3 before screening visit (Kurtzke, 1983) and before relapse (if applicable);
- Patients receiving treatment with IFN beta 1a 44 mcg TIW for at least 6 months but for no more than 10 years before the screening visit;
- Female patients must be neither pregnant nor breastfeeding and must lack childbearing potential as defined by either:
 - Postmenopausal or surgically sterile, or
 - Using a highly effective method of contraception for the duration of the study.

Furthermore, female patients must not have been pregnant from at least three months prior to enter in the study;

- Patients willing and able to comply with the protocol for the total duration of the study;
- Patients able to understand the purposes and the risks of the study;

- Patients have signed the appropriate written informed consent form, approved by the Independent Ethics Committee (IEC), prior to the performance of any study activities.

Patients with relapse must fulfil the additional following criterion to be eligible for this study:

- Deterioration of at least one step in a relevant functional system scale (FSS) (Visual, Brainstem, Pyramidal, Cerebellar and Ambulation score) or an increase in EDSS of 1 point or more compatible, according to physician's judgment, with the therapy prosecution;
- Relapse started within maximum 5 days before the inclusion in the study.

Patients without relapse must fulfil the additional following criterion to be eligible for this study:

- Clinically stable RR-MS.

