D-asp at the dose of 2660mg or placebo will be administered once a day for 24 weeks in the form of identical oral solution preparations. The IP (D-asp or placebo) should be administered preferably after the meal.

The content of a sachet should be cleared out in an empty glass. Then approximately 100 ml of still water should be added and the product should be mixed until the effervescence is ended. The product should be administered immediately after the preparation.

Placebo will be undistinguishable from D-asp in terms of packaging, size, colour, weight, appearance, taste and mode of administration.

6.3

Assignment to Treatment Groups

Patients presenting with a relapse and meeting the eligibility criteria during a screening period of 3-5 days will be randomised in a 1:1 ratio via e-CRF to:

- D-asp,
- Placebo.

It is planned to randomise 80 patients with relapse. Randomisation will be stratified according to age (<30 years vs. \geq 30 years) and site location (Rome+Naples+Pozzilli vs. the other sites).

Patients without a relapse will be recruited only at the Pozzilli site and will be randomised in a 1:1 ratio via e-CRF to:

- D-asp,
- Placebo.

It is planned to randomise 40 patients without a relapse. Randomisation will be stratified according to age (<30 years vs. \geq 30 years)

The randomisation list will be in a balanced block design and will be centralized. In each site, eligible patients will be sequentially assigned to the next study number as they present themselves for the study, starting from the lowest number provided for each centre. If a patient discontinues from the study, the patient number will not be reused, and the patient will not be allowed to re-enter the study.

It will be the responsibility of the Investigator (or designee) to explain, and make sure patients fully understand any appropriate treatment related information.

6.4

Non-investigational Medicinal Products to be Used

Treatment with the IP (D-asp 2660mg once daily or placebo) will be administered as add-on to conventional therapies (IFN beta-1a 44mcg TIW for patients without relapse and IFN beta-1a 44mcg TIW plus methylprednisolone i.v. for patients with relapse, for 5 consecutive days at 1000mg once daily).

The prescription of IFN beta-1a in the individual patients will be totally independent from his/her inclusion in the study.

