Therefore, each potentially eligible patient will be informed of the study's objectives and overall requirements. Before conducting any of the pre-entry tests not performed routinely in the patient's treatment, the Investigator will explain the study fully to the patient using the Informed Consent Form. If the patient is willing to participate in the study, he/she will be requested to give written informed consent after being given sufficient time to consider his/her participation and the opportunity to ask for further details. The Informed Consent Form will be signed and personally dated by both the patient and the Investigator/Co-Investigator. A copy of the signed form will be provided to the patient and the original will be retained with the source documents. Although nursing staff may be involved in describing the study to a patient, the Investigator/Co-Investigator must participate in discussions with the patient and must sign and personally date the Informed Consent Form.

Patients that will take part in the Neurophysiological assessments (patients without relapse enrolled in the centre of [PPD](#) [REDACTED]) and in the immune-phenotype and immunometabolic analysis (patients enrolled in the centres of Rome, Naples and Pozzilli) will sign a further specific Informed Consent Form.

A screening log will be completed for all patients who sign the Informed Consent Form but do not subsequently enter the study. Patients will be identified by their initials and dates of birth; in addition, each patient's gender and reasons for exclusion from the study will be recorded.

Patients meeting the eligibility criteria during the 3-5 days of Screening period will be assessed at baseline (Visit 0, Day 0-Week 0), and after 8 (Visit 1), 12 (Visit 2) and 24 (Visit 3) weeks from the first day of treatment with D-asp/placebo. The Baseline visit (Visit 0) will take place within 3-5 days from the screening visit (Visit -1). A \pm 3-day window is allowed for the planned days of the post-baseline visits.

An ET visit will be arranged for the patients that withdraw from the study at any time: they will undergo all assessments requested at the ET Visit as soon as possible after the study discontinuation.

Screening Period (Visit -1, Day -5/-3)

A complete pre-study evaluation (Screening visit, Visit -1) will be performed within 3-5 days prior to Baseline to include:

- Written Informed Consent prior to conducting any protocol assessments;
- Demographics data;

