- Medical history/present conditions;
- History of MS, date of first attack, date of MS diagnosis, number of clinical relapses, date of the last clinical relapse;
- Previous (in the last 12 weeks) and concomitant medications for the treatment of MS and other concomitant diseases will be recorded;
- Physical examination including height, weight, body mass index (BMI), waist circumference, blood pressure, heart rate;
- Neurological examination;
- For female patients, the contraceptive method used will be recorded, or, alternatively, if applicable, the age at menopause will be documented;
- A blood sample will be collected for haematology and blood chemistry tests, according to local clinical practice;
- A urine sample will be collected for routine urinalysis, according to local clinical practice;
- Serum pregnancy test, if applicable (is not required if the patient is postmenopausal or surgically sterilized);
- Administration of the EDSS;
- Administration of the 25-FWT, the 9HPT, the Symbol Digit Modalities Test and the Low Contrast Letter visual Acuity Test;
- Administration of the MFIS and of the Fatigue Severity Scale;
- Review of Inclusion/Exclusion Criteria;
- A 12-lead ECG will be performed whenever possible, according to local clinical practice;
- A brain MRI will be performed whenever possible, according to local clinical practice;
- Adverse events occurred from the signature of informed consent will be recorded;

A patient who fails to meet the protocol-specified criteria for study entry during the screening period is a screen failure. The date at which it was determined will be collected on the study entry e-CRF.

Should a patient be withdrawn from the study, his/her identification number will not be reallocated.

Once all procedures and assessments for this visit are completed, an appointment for the Baseline visit (Visit 0, 3-5 days after the Screening visit) will be made.

Baseline Visit (Visit 0, Day 0-Week 0)

The following procedures and assessments will be performed at this Visit:

- Confirmation that Inclusion/Exclusion Criteria are satisfied;
- Any change in concomitant medications will be recorded;
- Physical examination including height, weight, BMI, waist circumference, blood pressure, heart rate;
- Neurological examination;

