The MFIS is a modified form of the Fatigue Impact Scale (Fisk et al, 1994) based on items derived from interviews with MS patients concerning how fatigue impacts their lives. This instrument provides an assessment of the effects of fatigue in terms of physical, cognitive, and psychosocial functioning. The full-length MFIS consists of 21 items. The total score for the MFIS is the sum of the scores for the 21 items. Individual subscale scores for physical, cognitive, and psychosocial functioning can also be generated by calculating the sum of specific sets of items.

The Fatigue Severity Scale is a self-report questionnaire designed to assess disabling fatigue in all individuals (Krupp et al, 1989). The Fatigue Severity Scale consists of 9 questions, uses a 7-point Likert scale ranging from strongly disagrees to strongly agree.

Scoring procedures of the MFIS and of the Fatigue Severity Scale are described in [Appendix IV](#) and [Appendix V](#), respectively.

Generally, to maximize data consistency, the same physician should evaluate the same patient on the same assessments at approximately the same time of day, whenever possible. The assessments must be performed without consulting the results of the prior visit.

Details on the immune-phenotype and immunometabolic analysis performed in patients enrolled in the centres of Rome, Naples and Pozzilli are given in [Section 7.6](#).

Details on neurophysiological assessments performed in patients without relapse enrolled at the centre of the [PPD](#) are given in [Section 7.7](#).

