8.1 Sample Size

The primary study endpoint in the part of the study focused on relapsed patients is defined as the proportion of patients who, following a disease relapse associated with a worsening in their MS-related disability, return to baseline status within 8 weeks. Disability will be assessed through the Functional Systems Scores of the EDSS (Visual, Brainstem, Pyramidal, Cerebellar, Sensory, Bowel/Bladder and Ambulation score).

Available data from observational studies (Hirst et al, 2012) indicate that approximately 50% of the patients return to baseline EDSS within 2 months with standard treatments. Based on the fact that usually, in clinical studies where a rigid intention-to-treat (ITT) approach is used, a lower rate of responses/recoveries is observed as compared to observational studies, the expected rate of recovery at 2 months in the control group is set at 40%. With 40 patients per arm the study will be able to detect with 80% power, at the 0.05 alpha level (1-sided), an increase in the proportion of recovery at 2-months from 40% to 70%. The 1-sided significance level is justified by the exploratory nature of this study, aimed at generating study hypotheses to be tested in subsequent studies.

A total of 120 patients will be randomised to include the 40 RR-MS patients without relapses. This subgroup of patients without relapse has been included to assess whether D-Aspartate enhances LTP induction, by means of TMS

Refer to Section 6.3 for procedures of randomisation.

Eligible patients at the end of the screening period will be randomised in a 1:1 ratio to D-asp or placebo. Randomisation will be stratified according to age (<30 years vs. \geq 30 years) and site location (Rome+Naples+ Pozzilli vs. the other sites).

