EDSS steps from 0 up to 4.0 should not change compared to the previous examination, unless there is a change by one grade in at least one FS score. EDSS steps from 0 up to 1.5 can only apply if ambulation is "unrestricted". EDSS steps from 2.0 up to 5.0 are defined by the Functional System (FS) scores and/or walking range restriction. As an example, EDSS step 5.0 is possible with an unrestricted ambulation. EDSS steps from 2.0 up to 4.0 does only apply in individuals when at least "fully ambulatory" (able to walk ≥ 500 meters). If ambulation is assessed as "restricted" the pyramidal or cerebellar FS must be ≥ 2 . EDSS steps ≥ 5.5 are exclusively defined by the ability to ambulate, the assistance required or the use of a wheelchair.

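### The primary endpoint needs each relapse patient's pre-relapse Functional System and Ambulation scores, but the protocol does not require them to be recorded; separately, one phrase in 5.2 puts recovery on the EDSS instead

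*Combined protocol and SAP*

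**What the plan says.** **Endpoint.** Section 8.1 counts patients who, after a relapse that worsened their disability, "return to baseline status within 8 weeks". Disability is assessed on Visual, Brainstem, Pyramidal, Cerebellar, Sensory, Bowel/Bladder and Ambulation scores. The synopsis, 7.3, 8.2.1 and 8.2.2 name the same seven. None of these sections says which time point the baseline status refers to, or how many components must return.

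**Timing.** Section 6.3 states: "Patients presenting with a relapse and meeting the eligibility criteria during a screening period of 3-5 days will be randomised". Section 5.4 has eligibility met at screening and checked again at Visit 0, 3 to 5 days later. In Table 1 the row "Administration of EDSS" is marked at screening, Visit 0, Weeks 8, 12 and 24, and early termination. Visit 0 is the visit called Baseline.

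**History.** The 7.1 screening list asks for "History of MS, date of first attack, date of MS diagnosis, number of clinical relapses, date of the last clinical relapse". Neither 7.2 nor the patient-file list in 10.2 asks for earlier FS or EDSS scores.

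**Eligibility.** Section 5.3.1 admits "Patients with an expanded disability status scale (EDSS) score between 0 and 3 before screening visit" and before the relapse. Relapse patients must also show either a one-step worsening in one of five scores (Visual, Brainstem, Pyramidal, Cerebellar, Ambulation) or an EDSS rise of at least 1 point.

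**Scale.** A parenthesis in 5.2 describes the expected clinical gain as regaining the baseline EDSS. The control rate in 8.1 starts from observational data on return to baseline EDSS (about 50%) and is then set at 40%.

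**The concern.** An outcome defined as return to an earlier state needs that state on record. Here the earlier state lies before the first study contact, so only existing records can supply it, and the protocol neither asks for it nor names it as the reference. Read literally, Baseline is Visit 0, and a patient whose deficit had not changed since the relapse would count as having returned to it.

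The same reference is needed for recovery at Weeks 12 and 24 (8.2.2) and for time to recovery in the Cox model (8.4.2). If each site settles the question for itself, the comparator may come from different sources, be complete for some components only, or exist only as an EDSS step. The phrase in 5.2 adds to this, because it invites a comparison on EDSS where the endpoint is on component scores.

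**Working it through.** **1. Where the examinations fall.** Relapse patients must meet the relapse criteria at screening (5.4, 6.3), so onset precedes screening. Screening and Visit 0 are then both inside the relapse, and the remaining visits are outcome visits. No scheduled examination gives a pre-relapse score.

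**2. What the endpoint needs and what the text obliges.** With 80 relapse patients and seven components, 80 × 7 = 560 reference values are needed.

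| Source in the protocol | Pre-relapse component values it requires to be recorded |
|---|---|
| Table 1 and 7.1 visits | None (all after onset) |
| Screening history (7.1), 7.2, 10.2 | None (no prior scores listed) |
| Eligibility by EDSS rise | None; it can be checked on total EDSS |
| Eligibility by FS worsening | None; the check needs an earlier value for at least one of five scores |

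Sensory and Bowel/Bladder, two of the seven endpoint components, are outside the five.

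**3. Recovery must come from recorded values.** Section 7.3 states: "The assessments must be performed without consulting the results of the prior visit". A rater at Week 8 is therefore not placed to judge recovery against earlier results, so it has to be derived later from two recorded sets of scores.

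**4. EDSS and FS recovery can disagree.** A constructed patient, scored with the step definitions in Appendix II (other FS 0, ambulation unrestricted throughout):

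| | Pre-relapse | Visit 0 | Week 8 |
|---|---|---|---|
| Pyramidal | 2 | 2 | 2 |
| Cerebellar | 0 | 2 | 1 |
| Sensory | 0 | 2 | 1 |
| EDSS step | 2.0 | 3.0 | 2.0 |

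One FS at grade 2 with the others at 0 or 1 is step 2.0; three FS at grade 2 is step 3.0. The patient is eligible: EDSS 2.0 before relapse, a Cerebellar worsening, and an EDSS rise of 3.0 − 2.0 = 1.0. At Week 8 the EDSS is back to 2.0, so the patient has recovered on EDSS. On the components, Cerebellar and Sensory are both 1 against 0 before, so the patient has not recovered, whether the rule covers all seven components or only those that worsened. With only the EDSS step on file, the FS comparison cannot be made.

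**5. The planned sample size is not in error.** Inputs from 8.1: 40 per arm, 40% against 70%, one-sided alpha 0.05. The pooled rate is 0.55.
- SE under the null: √(0.55 × 0.45 × 2/40) = 0.1112.
- SE under the alternative: √((0.40 × 0.60 + 0.70 × 0.30)/40) = 0.1061.
- Uncorrected power: Φ((0.30 − 1.645 × 0.1112)/0.1061) = 86.5%.
- With a continuity correction of 1/40 = 0.025 taken from the difference: 80.7%, which matches the stated 80%.

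The only link to this point is that the 40% is an EDSS-based figure applied to an FS-based endpoint. The documents do not say whether the FS rate is higher or lower.

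**The case against.** **The scores probably exist.** Eligibility cannot be checked without some knowledge of pre-relapse status. Appendix II says EDSS steps up to 4.0 should not change "unless there is a change by one grade in at least one FS score", so FS grades should lie behind either entry route. Patients have had at least 6 months of interferon, attend MS centres, and were stable or improving for at least 30 days before the relapse; original records are kept. This stands, and it limits the harm. A reader might infer that the reference is lost and the endpoint cannot be computed. The documents do not support that. They do show that nothing obliges a site to retrieve all seven values, or to record their date and source.

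**The e-CRF may already ask for them.** It may, as may its completion conventions or the Manual of Operations. None is among the documents, so the point is confined to the protocol text.

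**The SAP can settle it.** Section 8.4.1 promises a SAP before database lock. It can fix the reference, the recovery rule and the handling of missing values, but it cannot guarantee that the values were collected.

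**The scale conflict is one phrase.** This is right. Every formal definition uses the FS scores, and 5.2 is a discussion of expected results. A reader might infer two competing primary endpoints, or that scoring fatigue within the Cerebral FS changes the result. Neither follows: the Cerebral FS is not an endpoint component, so fatigue scoring would matter only if EDSS were the endpoint.

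**Conclusion.** The point holds as a gap in required data capture and in the naming of the reference. It should be fixed before enrolment, because collection is the part that later analysis planning cannot guarantee. It rests on one inference, that baseline status in 8.1 means pre-relapse status; this is the only reading under which a return to it is a recovery.

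The gap touches the primary endpoint for all 80 relapse patients, together with the Week 12 and 24 recovery endpoints and the Cox analysis. How many patients would lack a usable reference is unknown. A reader might go on to infer a specific loss of power, but the documents give no missing share from which to compute one, and the chi-square test without continuity correction has 86.5% power at 40 per arm, so there is some reserve on that basis. The inconsistency in 5.2 is real but minor.

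**What to change.** 1. **Capture.** Add to the 7.1 screening list, Table 1 and the e-CRF the last documented pre-relapse score for each of the seven endpoint components plus EDSS, with date and source, abstracted from the chart before treatment assignment.
2. **Reference and rule.** In the synopsis, 7.3, 8.1, 8.2.1, 8.2.2 and 8.4.2, state that the reference is pre-relapse status, not Visit 0, and state one recovery rule. One option is every listed component at or below its pre-relapse value; a rule limited to the components that worsened is an alternative.
3. **Scale.** Reword the parenthesis in 5.2 to match the FS-based endpoint, and note in 8.1 that the 40% control rate is taken from EDSS-based data.
4. **Incomplete references.** Pre-specify the handling, for example counted as not recovered in the main ITT analysis, with a sensitivity analysis in patients whose reference is complete.

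The cost is one e-CRF page and wording in nine places (Table 1, 7.1, the synopsis, 5.2, 7.3, 8.1, 8.2.1, 8.2.2, 8.4.2), plus chart abstraction at the sites; no visit or examination is added. The drawback is that chart scores will differ in rater and date and some will be incomplete, so the change makes the reference explicit but only partly standardises it.
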